1. PURPOSE OF THE STUDY

a. Brief Summary

This study will test whether hemodialysis two times per week is equally effective as hemodialysis three times per week for people who still have some kidney function left. It will hopefully show that twice weekly hemodialysis provides the same quality of life as three times weekly hemodialysis. Such a finding could reduce the burden of hemodialysis and improve people's quality of life.

b. Objectives

More than 100,000 people start hemodialysis every year with the majority getting treatments three days per week. Many of these people, however, have enough remaining kidney function so that they may be able to receive hemodialysis treatments two days per week instead of three. We hope to learn whether a proposed formula for twice weekly dialysis prescription provides effective treatment for patients with residual native kidney function. This knowledge could hopefully reduce the burden on future patients and the cost of their treatment.

c. Rationale for Research in Humans

This study will assess the effect of twice weekly dialysis on the quality of life and on levels of uremic solutes in patients with residual native kidney function. Therefore, we need to include human subjects.

2. STUDY PROCEDURES

a. Procedures

Hemodialysis patients with sufficient residual native kidney function will undergo two 4-week study periods in a cross-over design. During these periods, hemodialysis will be prescribed three times per week and two times per week according to a formula put forward by a National Kidney Foundation Committee.

Screening:

- local nephrologists will be contacted to identify patients with measured residual kidney function or patients who report still producing urine.
- informed consent will be obtained from eligible patients.
- patients who consent will then undergo a run-in period followed by randomization into the cross-over study if they have adequate residual function.

Run-in period:

- patients' residual kidney function (Kru) will be measured by urine and blood collection.
- if Kru is >2.5 ml/min, patients will then proceed into the crossover study periods after completing the following steps:
 - receive extra dietary counseling in addition to routine dietary advice provided by the dialysis unit
 - diuretic doses will be optimized

Cross-over study with two 4-week study periods.

During each period:

- hemodialysis will be prescribed to achieve adequate treatment according to current National Kidney Foundation Committee guidelines.
- patients will be visited weekly.
- patients will continue to obtain blood work monitoring as per their routine dialysis care.
- hemodialysis and medications will be adjusted by the patients' primary nephrologist as needed.
- receive extra dietary counseling in addition to routine dietary advice provided by the dialysis unit

At the end of each 4-week period:

- patients' residual kidney function will be measured.
- pre- and post-treatment blood samples will be collected at the last treatment of the period. Blood will be collected through the dialysis tubing in the same fashion as the patients' routine lab monitoring.
- waste dialysate, which normally gets thrown away, will be collected during the last treatment.
- patients will complete symptom questionnaires and cognitive function tests.

b. Procedure Risks

Blood would be collected in the same sterile fashion as the patients' routine lab checks. Since the patients are on hemodialysis, blood will be collected in the same fashion as their routine monthly labs through the hemodialysis tubing. We will monitor levels of common blood chemistry such as serum potassium and CO₂ as well as monitor blood pressure and weights during the study. We will adjust the hemodialysis prescription and medications based on this monitoring. We will visit the patients weekly to monitor for any symptoms. Hemodialysis will be prescribed according to current National Kidney Foundation Committee guidelines to ensure adequate treatment for the patients.

c. Will it be possible to continue the more (most) appropriate therapy for the participant(s) after the conclusion of the study?

Yes

d. Study Endpoint(s)

The primary endpoint is quality of life as assessed by the KDQOL-36, a questionnaire designed to assess the symptoms commonly experienced with kidney disease. Other endpoints are an additional symptom questionnaire (Dialysis Symptom Index), cognitive testing (Trails Making B and Digit Symbol Substitution Test), and plasma levels of

uremic solutes. We are testing for equivalency between two approved ways of prescribing the hemodialysis. A Data Safety Monitor will review results regularly and report to us and the IRB on any departure from this expectation. If no unexpected differences are detected, the study will end once the projected total subject population has completed the study.

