Efficacy of Twice Weekly Hemodialysis in Patients With Residual Kidney Function

NCT03874117

April 30, 2025

Data Analysis Plans

The prespecified primary outcome is the quality of life assessed by the KDQOL-36. Secondary outcomes are symptom burden assessed by the Dialysis Symptom Index, cognition assessed by the Trails Making B Test and Digit Substitution Test, and plasma solute levels. Equivalence between twice weekly and thrice weekly hemodialysis will be assessed based on the KDQOL-36 score using a mixed-effects model with a random intercept to take into account the repeated measures per patient. Treatment-by-period effect will be first tested by adding a treatment-by-period interaction; if nonsignificant, the treatment effect will be estimated with period and treatment as the covariates, and if significant, the treatment effect will be estimated using a linear regression model with data from the first period only. A two-sided 90% confidence interval (CI) will be calculated and equivalence concluded if the CI is contained within the prespecified margin of -5 and 5 for the KDQOL-36 score. For analysis of other outcomes, we will compare means using a mixed-effects model and medians using quantile regression with robust standard errors to account for the multiple observations per patient. The mixed-effects model assumed data to be missing at random while quantile regression assumed data to be completely missing at random. All analysis assumed 5% significance.

Rationale for Sample Size

The power calculation was based on a previous study in which repeat measures of the KDQOL-36 score at six weeks in a group of control hemodialysis patients had a paired difference of 2.1 ± 5.7 compared to the original value. Based on this finding, 30 patients would provide more than 90% power to test whether twice weekly hemodialysis was equivalent to thrice weekly hemodialysis with the equivalence margin defined as -5 and 5. The equivalence margin (γ) was chosen based on previous studies showing no association with adverse outcomes with this degree of reduction.

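### No KDQOL-36 before randomization is described, so the SAP's first-period fallback is an unadjusted between-patient comparison; a run-in score would strengthen it cheaply, with a small effect on overall power

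*Protocol*

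**What the plan says.** Protocol section 2a (Procedures) gives the run-in content. First, "patients' residual kidney function (Kru) will be measured by urine and blood collection"; patients above the Kru threshold then get dietary counseling and have diuretics optimized before the crossover. No questionnaire appears there. The statement that "patients will complete symptom questionnaires and cognitive function tests" stands only in the list for the end of each 4-week period. Section 2d (Study Endpoints) says "The primary endpoint is quality of life as assessed by the KDQOL-36". Taken together, each patient has two primary-outcome values, both after randomization.

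The SAP (Data Analysis Plans) tests the treatment-by-period interaction first and, "if significant, the treatment effect will be estimated using a linear regression model with data from the first period only". No baseline or other covariate is named for that regression. The decision rule is the same on either branch: "A two-sided 90% confidence interval (CI) will be calculated", and equivalence is concluded if it is "contained within the prespecified margin of -5 and 5 for the KDQOL-36 score". The sample-size rationale claims more than 90% power with 30 patients, from a previous study whose repeat scores "had a paired difference of 2.1 ± 5.7 compared to the original value". No power is given for the first-period branch.

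**The concern.** The sample size rests on within-patient differences. The fallback discards the pairing and compares different patients, so stable differences in quality of life between patients enter the standard error. Without a pre-randomization score, nothing in the planned data on the primary outcome can remove that variance. The interaction test can also come out significant by chance, in which case the primary conclusion passes to a far less precise comparison judged against the same ±5 margin. A single questionnaire during run-in would recover part of the lost precision.

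**Working it through.** **Inputs from the documents.** Margin ±5; two-sided 90% CI; general 5% significance level, applied here to the interaction test; 30 patients; paired spread 5.7, read as an SD because the SAP does not label it; about 50 enrolled before the Kru check (Protocol 5a).

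**Assumptions.** 1:1 allocation to sequences, so 15 vs 15; no dropout; zero true difference; no carryover; between-patient SD (SDb) from 4 to 18, because the documents give none; a run-in score that correlates with the period 1 score as strongly as the repeat measures behind the 5.7.

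**Step 1: the plan's own figure.** SE = 5.7/√30 = 1.04. Power of the two one-sided t-tests at zero difference is 99.8%, so the claim of more than 90% reproduces. (If the true difference were 2.1 it would be about 86%. Zero is used below, which favors the plan.)

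**Step 2: the unadjusted fallback, ignoring the trigger.** Within-patient variance = 5.7²/2 = 16.2, so the within-patient SD is 4.0. The SD of a single score is √(SDb² + 16.2). The 90% CI half-width is 1.701 × √(2/15) × SD = 0.621 × SD, with 28 df.

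| SDb | SD of one score | Half-width | Power |
|---|---|---|---|
| 4 | 5.7 | 3.5 | 52% |
| 6 | 7.2 | 4.5 | 18% |
| 8 | 9.0 | 5.6 | 2.5% |
| 12 | 12.7 | 7.9 | about 0% |
| 18 | 18.4 | 11.5 | about 0% |

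**Step 3: condition on the trigger.** With two periods, the interaction is tested by the sequence difference in patient totals. Its correlation with the first-period difference is √((1 + ρ)/2), where ρ = SDb²/(SDb² + 16.2). At SDb 8, ρ = 0.80 and the correlation is 0.95. A significant test needs a contrast beyond 2.05 SE, so the first-period difference is expected to be at least about 0.95 × 2.05 × 3.27 = 6.4 points from zero, where 3.27 = 9.0 × √(2/15). That is already outside the margin. In simulation of this model (200,000 trials per setting), unadjusted power given a chance trigger was about 5% at SDb 4 and about 0% from SDb 6.

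**Step 4: add the baseline covariate.** The residual SD is SD × √(1 − ρ²). Ignoring the trigger, this gives a half-width of 3.1 to 3.5 and power of 71% (SDb 4) to 53% (SDb 18). Given a chance trigger, simulated power is about 27% at SDb 4, 30% at SDb 8, 32% at SDb 12 and 35% at SDb 18.

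**Step 5: the whole procedure.** Without carryover the trigger rate is 5%. Overall power ≈ 0.95 × 0.998 + 0.05 × (fallback power given trigger). At SDb 8 this is 0.948 + 0.05 × 0 = 94.8% without the covariate and 0.948 + 0.05 × 0.30 = 96.3% with it. Over the SDb range the gain is about 1 to 2 percentage points.

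**Step 6: more patients randomized.** If all 50 enrolled passed the Kru check (25 vs 25, an upper bound), adjusted power given a chance trigger is about 68% at SDb 8 and 73% at SDb 12. The overall gain is about 2 to 4 points.

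**The case against.** The best case against acting is that the weakness belongs to the pretest rule and the missing questionnaire is secondary. The fallback is rare without carryover, the two-stage procedure as written keeps about 95% power at zero difference, and a baseline score leaves a chance-triggered fallback failing about two times in three at 15 vs 15. If the rule were removed, the complete-pair crossover analysis would gain little from the extra score. All of this stands, and it limits the point to an inexpensive improvement. It does not remove the point, because the SAP keeps the rule and the covariate clearly improves that branch.

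It can also be said that the missing run-in score is inferred from a short procedures list that does not name the KDQOL-36 at any visit. That is fair. If a run-in score is in fact collected, the remaining gap is that the SAP does not use it.

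A reader might infer more in three ways, none of which the documents support:

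- That the fallback has almost no chance of meeting the margin, as a plain fact. Ignoring the trigger, this needs a between-patient SD of about 8 or more, and the documents give none; at SD 4 the figure is 52%.
- That a baseline score would restore the planned power. It would not at 15 vs 15, even before conditioning on the trigger.
- That a run-in score would materially help with early dropouts. A patient with only a pre-treatment value adds almost nothing to the treatment contrast, no dropout rate is given, and the SAP contains no missing-data sensitivity analysis into which the value could go.

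**Conclusion.** The point holds as an optional improvement. As described, the first-period fallback is an unadjusted between-patient comparison of about 15 vs 15. At every between-patient SD examined its power is far below the stated 90%, and after a chance trigger it is about 5% at best. A pre-randomization KDQOL-36 used as a covariate raises that to roughly 30%, or about 70% if 25 vs 25 are randomized. The effect on the trial as a whole is small while the trigger rate stays near 5%. Real carryover would trigger the rule more often, but the documents give no basis for sizing it. The figures depend on the assumed between-patient SD, 1:1 allocation, zero true difference and the baseline correlation. The direction of the gain is the same across the whole SD range.

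**What to change.** In Protocol section 2a, add one KDQOL-36 at the end of run-in, after the Kru check and the other listed run-in steps and before randomization. This timing avoids collecting it from patients who do not proceed, and avoids a score that predates the run-in changes. In the SAP, if the first-period rule is kept, name that score as a covariate in the first-period regression. If a run-in score is already collected, say so and name it there.

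The cost is a few minutes of patient time and one extra model term. Treatment and the complete-pair crossover analysis are unchanged. The change helps only patients not yet randomized, and it brings little if the sponsor removes the first-period rule.

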3. BACKGROUND

a. Past Experimental and/or Clinical Findings

We have previously found that the residual native kidney can control plasma levels of secreted solutes better than those of the index solute urea. We subsequently found that plasma levels of secreted solutes were lower or the same in patients on twice weekly hemodialysis compared to anuric patients on thrice weekly hemodialysis.

b. Findings from Past Animal Experiments

N/A

4. DRUGS, BIOLOGICS, REAGENTS, OR CHEMICALS USED IN THE STUDY

a. Commercial Drugs, Biologics, Reagents, or Chemicals

None

5. PARTICIPANT POPULATION

a. Planned Enrollment

Approximately 50 subjects expected to be enrolled from Stanford-affiliated sites including VA Palo Alto, Satellite Healthcare, and Santa Clara Valley Medical Center.

b. Age, Gender, and Ethnic Background

The age range will be 18 to 85 years old. The gender and ethnic background will be representative of the Bay Area population.

c. Recruitment Details

We will notify the primary nephrologists who will help identify patients who are on hemodialysis and have residual kidney function. Residual kidney function (Kru) is not routinely measured. For those patients who do have Kru measured, they will be eligible for the study if Kru is >2.5 ml/min. If no Kru has been measured, a report of urine production greater than 500 ml/day (about 1 cup/day) is sufficient. All patients who consent to be in the study will then provide 24-hour urine and blood collection during the run-in period as described in the study procedures to obtain a Kru measurement before they proceed into the study periods. If the measured Kru is >2.5 ml/min, they can proceed into the study periods. If the measured Kru is <2.5 ml/min, they will not proceed further with the study.

d. Eligibility Criteria

i. Inclusion Criteria

- patients on hemodialysis who have residual kidney function with residual urea clearance (Kru) >2.5 ml/min.

- been on hemodialysis for at least 3 months.
 - adherence to regular dialysis treatments.
- ii. Exclusion Criteria
- inability to achieve adequate hemodialysis.
 - planned revision of hemodialysis vascular access.
 - hospitalized within the past 2 months.
-

e. **Screening Procedures**

We will notify the primary nephrologists who will help identify patients who are on hemodialysis and have residual kidney function. Residual kidney function (Kru) is not routinely measured. For those patients who do have Kru measured, they will be eligible for the study if Kru is >2.5 ml/min. If no Kru has been measured, a report of urine production greater than 500 ml/day (about 1 cup/day) is sufficient.

Efficacy of Twice Weekly Hemodialysis in Patients With Residual Kidney Function

NCT03874117

April 30, 2025

Data Analysis Plans

The prespecified primary outcome is the quality of life assessed by the KDQOL-36. Secondary outcomes are symptom burden assessed by the Dialysis Symptom Index, cognition assessed by the Trails Making B Test and Digit Substitution Test, and plasma solute levels. Equivalence between twice weekly and thrice weekly hemodialysis will be assessed based on the KDQOL-36 score using a mixed-effects model with a random intercept to take into account the repeated measures per patient. Treatment-by-period effect will be first tested by adding a treatment-by-period interaction; if nonsignificant, the treatment effect will be estimated with period and treatment as the covariates, and if significant, the treatment effect will be estimated using a linear regression model with data from the first period only. A two-sided 90% confidence interval (CI) will be calculated and equivalence concluded if the CI is contained within the prespecified margin of -5 and 5 for the KDQOL-36 score. For analysis of other outcomes, we will compare means using a mixed-effects model and medians using quantile regression with robust standard errors to account for the multiple observations per patient. The mixed-effects model assumed data to be missing at random while quantile regression assumed data to be completely missing at random. All analysis assumed 5% significance.

Rationale for Sample Size

The power calculation was based on a previous study in which repeat measures of the KDQOL-36 score at six weeks in a group of control hemodialysis patients had a paired difference of 2.1 ± 5.7 compared to the original value. Based on this finding, 30 patients would provide more than 90% power to test whether twice weekly hemodialysis was equivalent to thrice weekly hemodialysis with the equivalence margin defined as -5 and 5. The equivalence margin (γ) was chosen based on previous studies showing no association with adverse outcomes with this degree of reduction.

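### The primary analysis pre-tests the treatment-by-period interaction and may switch to first-period data, so its 90% confidence interval does not have 90% coverage

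*SAP*

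**What the plan says.** Protocol section 2a sets the design: patients "will undergo two 4-week study periods in a cross-over design". It describes no washout, and the questionnaires are completed at the end of each period.

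Under Data Analysis Plans, the SAP makes the primary KDQOL-36 analysis a two-step rule. First, "Treatment-by-period effect will be first tested by adding a treatment-by-period interaction". If that is not significant, the estimate comes from a random-intercept mixed model with treatment and period. Otherwise, "if significant, the treatment effect will be estimated using a linear regression model with data from the first period only". Whichever branch is taken, one two-sided 90% interval is compared with -5 and 5, and nothing adjusts it for the data-driven choice.

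The pre-test has no level of its own; the only statement is "All analysis assumed 5% significance". Under Rationale for Sample Size, the SAP says "30 patients would provide more than 90% power to test whether twice weekly hemodialysis was equivalent to thrice weekly hemodialysis". That power rests on the SD of paired differences, and no power is given for the first-period branch.

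**The concern.** In a two-treatment, two-period crossover, the treatment-by-period interaction is the same contrast as the difference between the two sequence groups in patient totals. It is a between-patient comparison. If there is no carryover, a significant result means only that one sequence group happened to score higher overall.

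The first-period comparison is also between patients, and it contains the same imbalance. The rule therefore tends to pick the first-period estimate when that estimate is far from the truth, and then attaches an ordinary interval as if no selection had taken place. The both-period estimate, which the rule discards, is unaffected by the imbalance.

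At stake is the interval that decides the trial's main conclusion.

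**Working it through.** **Inputs.** From the SAP: n = 30 (taken as 15 per sequence), paired SD 5.7, margin ±5, 90% interval, 5% pre-test. The within-patient correlation ρ is not in the documents and is assumed at 0 to 0.9. Data are taken as normal and complete.

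**The plan's own figure.** SE = 5.7/√30 = 1.041. Power at true difference 0 is 2Φ(5/1.041 − 1.645) − 1 = 99.8%, which agrees with the SAP's claim of more than 90%. At a true difference of 2.1 it is 87.3% (normal) or 85.9% (t).

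**Why the selection matters.** Let σ be the SD of one score, S = Y1 + Y2 and D = Y1 − Y2.
- Cov(S, D) = 0, so the both-period estimate, built from D, is independent of the pre-test, built from S.
- Corr(Y1, S) = σ²(1+ρ) / [σ · σ√(2(1+ρ))] = √((1+ρ)/2). This is 0.71 at ρ = 0, 0.87 at 0.5 and 0.97 at 0.9.

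**Interval widths.** The t quantile on 28 df is 1.701.
- Both-period half-width: 1.701 × 1.041 = 1.77.
- First-period half-width: 1.701 × σ√(2/15), with σ = 5.7/√(2(1−ρ)).

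**No carryover.** The last four columns come from simulation, 100,000 trials per setting. The pre-test is a t-test on patient sums with n − 2 df.

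| ρ | σ | First-period half-width | Coverage after a false switch | Overall coverage | Equivalence shown after a false switch, difference 0 | False equivalence at difference 5, all trials |
|---|---|---|---|---|---|---|
| 0 | 4.03 | 2.50 | 52% | 88% | 58% | 6.0% |
| 0.3 | 4.82 | 2.99 | 37% | 87% | 22% | 6.3% |
| 0.5 | 5.70 | 3.54 | 27% | 87% | 4-5% | 6.5% |
| 0.7 | 7.36 | 4.57 | 16% | 86% | 0.2% | 5.8% |
| 0.8 | 9.01 | 5.60 | 9% | 86% | 0% | 4.9% |
| 0.9 | 12.75 | 7.92 | 3% | 86% | 0% | 4.8% |

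On the same falsely switched trials, the both-period interval covers about 90% and shows equivalence at difference 0 in over 99%. Overall coverage can be checked by hand. At ρ = 0.5 it is 0.95 × 90% + 0.05 × 27% = 86.9%.

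False equivalence does not rise at ρ of 0.8 or more because the expected first-period half-width (5.60, 7.92) already exceeds the margin of 5.

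Over all trials, missed equivalence at difference 0 goes from 0.2% to 2-5%. Power at 2.1 falls from 86% to 81-84%; this is illustrative only, since 2.1 is a control group's change over six weeks and not a treatment effect.

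**With carryover.** Here 5 points are added in period 2 to the sequence that starts with twice weekly, masking a true difference of 5. The both-period model then gives 76% false equivalence and about 24% coverage at every ρ.

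| ρ | Pre-test detects it | False equivalence, SAP rule | Coverage, SAP rule |
|---|---|---|---|
| 0 | 64% | 28% | 67% |
| 0.3 | 40% | 46% | 50% |
| 0.5 | 27% | 55% | 39% |
| 0.7 | 16% | 63% | 32% |
| 0.8 | 12% | 66% | 28% |
| 0.9 | 8% | 69% | 25% |

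With a 2-point carryover, false equivalence is 24% (both-period) against 20-23% (SAP rule), and coverage is about 76% against 72-76%.

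**Sensitivity.** Protocol section 5a says "Approximately 50 subjects expected to be enrolled", before residual function is confirmed. At n = 50 without carryover, overall coverage is again 86-88%, coverage after a false switch 51% to 3%, and false equivalence 4.8-6.5%. With the masking 5-point carryover, false equivalence is 92% (both-period) against 54% (ρ = 0.5) and 82% (ρ = 0.9) under the rule. A 10% pre-test at n = 30 gives overall coverage of 83-86% for ρ from 0.3 to 0.9.

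**The case against.** The strongest reply is that the rule changes the trial's decision very little. False equivalence stays within about 1.5 points of 5%, power at difference 0 stays above 90%, and most of the harm is missed equivalence, the conservative direction for an equivalence claim. The very low coverage figures are conditional on an event with a 1-in-20 chance. All of this stands, and it is why the overall effect is called moderate.

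The second reply is that the rule does protect against real carryover. With a 5-point carryover it beats the both-period model in coverage and in false equivalence at every ρ, clearly so at low ρ. No washout is described, and the documents give no evidence on carryover, so they cannot settle which scenario matters more. This also stands, and removing the rule is a real trade-off. But at ρ of 0.5 or more the pre-test finds a 5-point carryover in at most 27% of trials, and more than half still end in false equivalence. At 2 points the rule gains nothing in coverage. It is a weak safeguard, and a non-significant pre-test could wrongly reassure.

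Third, ρ is assumed, and the 5% pre-test level is inferred from a general sentence. The conditional figures do move widely with ρ. The direction of the effect and the overall loss of 2-4 points do not depend on it, and a 10% pre-test makes the loss larger.

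**Conclusion.** The concern holds. As written, the primary 90% interval has 86-88% coverage when there is no carryover, and 52% down to 3% in the 5% of trials that are switched by chance, although a valid interval was available in those same trials. The SAP's power statement survives at a true difference of 0, and false equivalence is only slightly affected. This should be fixed, but it does not invalidate the design. The result assumes two equal sequence groups, normal complete data, the SAP's paired SD, a 5% pre-test and ρ between 0 and 0.9.

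**What to change.** Delete the pre-test and the switch. Make the both-period mixed model (treatment and period fixed, patient random intercept) the single primary analysis. Report the sequence/carryover contrast and the first-period estimate, with intervals, as sensitivity results that do not drive the equivalence decision.

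State the absence of carryover as an assumption and give its basis, namely measurement at the end of each 4-week period, with no washout described. That is an argument and not proof, so add a tipping-point check. Carryover shifts the both-period estimate by half its size, so the carryover that would reverse the conclusion is 2 × (distance from the nearer interval limit to the margin). With the expected half-width of 1.77, this is 2 × (5 − 0 − 1.77) = 6.5 points for an observed difference of 0, and 2 × (5 − 2.1 − 1.77) = 2.3 points for 2.1.

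The change needs a few sentences and an extra sensitivity report, with no new patients or data. Its statistical cost is the partial protection against a large carryover set out above. The SAP is dated April 30, 2025 and is partly in the past tense. If outcome data have already been seen, the change is post hoc: date it, disclose it and report both analyses.

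### Does the primary rule leave the trial without a conclusion if twice-weekly dialysis turns out better by more than the margin?

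*SAP*

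**What the plan says.** The aim is two-sided wherever it is stated. Protocol section 1a (Brief Summary) says: "This study will test whether hemodialysis two times per week is equally effective as hemodialysis three times per week". Protocol section 2d (Study Endpoint(s)) says: "We are testing for equivalency between two approved ways of prescribing the hemodialysis".

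The SAP, under Data Analysis Plans, turns this into one rule, applied to a two-sided 90% interval for the treatment difference: "equivalence concluded if the CI is contained within the prespecified margin of -5 and 5 for the KDQOL-36 score". If the treatment-by-period interaction is significant, "the treatment effect will be estimated using a linear regression model with data from the first period only".

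Under Rationale for Sample Size, the margin is supported by earlier studies "showing no association with adverse outcomes with this degree of reduction". The same section gives the planning variability: control patients measured twice "had a paired difference of 2.1 ± 5.7 compared to the original value".

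Neither document mentions non-inferiority, and neither states which treatment is subtracted from which.

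**The concern.** A 90% interval inside ±5 amounts to two one-sided tests at 5%. One excludes a 5-point loss, the other a 5-point gain. Fewer dialysis sessions are a lighter burden, so a clinician mainly wants to know that quality of life does not fall, and the SAP's reason for the margin speaks only of a fall. Yet the rule needs both tests to pass. A result in favour of twice-weekly dialysis whose upper limit crosses +5 gets the same label as one whose lower limit crosses -5.

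If that were a real gap, the trial could show that fewer sessions do not cost 5 points and still have no prespecified way to say so. The statement would be open to the charge of being post hoc, although the planned analysis already contains the test for it.

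**Working it through.** **Inputs.** Margin ±5, two-sided 90% interval and 30 patients (SAP). Paired-difference SD 5.7 (SAP; the ± is taken to be an SD). The two-period model with a period term leaves 28 degrees of freedom. Positive is taken to mean better on twice-weekly dialysis; the SAP does not define the sign.

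**The plan's own figure.** The SAP states more than 90% power. A paired two-one-sided-tests calculation (n = 30, SD 5.7, 5% per side, exact t) gives 99.8% at a true difference of zero, so the statement is reproduced there. At a true difference of 2.1 it would be 86%. The power claim therefore needs a true difference at or near zero, although the SAP does not say so.

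**Where the rule bites.**

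- Standard error = 5.7/√30 = 1.041.
- 90% half-width = 1.701 × 1.041 = 1.77.
- Equivalence needs an estimate within ±(5 − 1.77) = ±3.23.
- An estimate of +3.35 gives about +1.6 to +5.1: a 5-point loss is excluded, and equivalence is not concluded.

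**How often that happens.** Approximately, the chance is 1 − Φ((3.23 − δ)/1.041) for a true benefit δ. At δ = 3 this is 1 − Φ(0.22) = 0.41. The exact figures (28 df) are the probability that the lower limit is above −5 minus the probability that equivalence is concluded:

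| True benefit | Equivalence concluded | Loss excluded, equivalence not concluded |
|---|---|---|
| 0 | 99.8% | 0.1% |
| +1 | 98.2% | 1.8% |
| +2 | 87.8% | 12% |
| +3 | 59.1% | 41% |
| +4 | 24.0% | 76% |

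With 50 patients completing, the last column is 2% at +2 and 21% at +3. With 30 patients and an SD of 8, which is an assumption not found in the documents, it is 36% and 62%.

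**Are the larger benefits planned for?** No. The 2.1 in the SAP is a change over six weeks in control patients, not an expected gain from twice-weekly dialysis. The hope in Protocol section 1a of improving quality of life describes what a finding of equivalence might lead to.

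**Does the plan fall silent?** No. An interval crossing +5 means that equivalence is not concluded. If the true benefit is +4, a low chance of concluding equivalence within ±5 is how an equivalence test should behave close to its margin.

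**What a non-inferiority claim would cost.** In the two-period analysis the lower test is already one of the two planned tests, so declaring non-inferiority there adds no error. The first-period fallback is different. A simulation of 400,000 trials per setting assumed 15 patients per sequence, no carry-over, a true difference of −5, an interaction pretest at 5%, and between-patient SDs of 10, 15 and 20 (not in the documents):

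- If the claim followed whichever analysis is used, false non-inferiority would be 7.1% to 7.3%.
- If it were restricted to the two-period analysis, it would be 4.7% to 4.8%.
- The planned equivalence rule gives 4.7% to 4.8% as it stands.

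**The case for a change.** The strongest case is that the addition is almost free. The lower test is already in the plan, no patients are needed, and equivalence would stay primary. The only reason given for the margin concerns a reduction, so nothing explains the +5 side. The undefined sign leaves the reader to infer which limit stands for harm.

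Part of this stands. A nested non-inferiority statement would be valid in the two-period analysis, and a sentence fixing the direction of the difference would help the reader. But a rule symmetric at ±5 gives the same decision whichever way the subtraction is done, so the missing sign changes no planned conclusion. A rationale that covers only one side leaves the other unexplained without making it wrong: a question about equivalence needs an upper limit.

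Nor is the addition free of dispute. It would declare non-inferiority at one-sided 5%, where some readers expect 2.5%. It would have to be barred from the first-period fallback to avoid an error of about 7%, and the equivalence decision in that fallback would then need separate wording. Its value also depends on being fixed before results are seen. The SAP is dated April 30, 2025, and the documents do not show whether data had been seen by then. If they had, the added claim would itself be post hoc.

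**Conclusion.** The concern does not hold. The symmetric rule matches the stated aim, gives a defined conclusion for every result, and hides nothing, because the interval shows which limit failed. What is absent is a second claim that the investigators did not set out to make, and whether to add it is a matter of preference.

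The chance of excluding a 5-point loss while missing equivalence is 0.1% at zero difference and 1.8% at +1. It becomes substantial only at benefits of +2 or more, which the documents do not project. These figures assume 30 patients in the two-period analysis, normal paired differences, and 5.7 as the SD of the paired difference. A larger SD would widen the gap, but it would not make the rule wrong for the question asked.
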